As part of the clinic-based testing for the study, participants will be asked to (1) complete online surveys with validated patient-reported questionnaires about their pain and function. The single-session of education and instruction (load modification vs standard exercise) will be performed by a licensed physical therapist immediately after the testing procedures are complete. Participants will undergo the same clinic-based testing protocol at the 4-week follow-up prior to their visit with the physician in the Jameson Crane Sports Medicine Institute at OSUWMC. For 4-weeks following the initial evaluation and clinic-based testing, participants will be asked to complete weekly online/telephone surveys to document their hip pain and function as well as their compliance with the prescribed home exercise program. Key variables of interest (Table 2) include the Global Rating of Change scale¹⁸ and the Numeric Pain Rating Scale^{18,33,34}. The other secondary variables of interest will help us more completely assess the effect of the proposed program hip function questionnaires, overall function,³⁵⁻³⁷ activity level,³⁸ and self-efficacy.³⁹

Table 2. Variables of Interest

[figure not shown]
Primary VOIs	Secondary VOIs
Global Rating of Change (GROC) (Mellor 2016)	Frontal plane kinematics of the trunk, pelvis, hip, and knee during a single leg squat
Numeric Pain Rating Scale (NPRS) (Farrar 2010, Fearon 2017, Mellor 2016)	Victorian Institute of Sport Assessment for Greater trochanteric pain syndrome (VISA-G) (Fearon 2014)
	Pain Self-Efficacy Questionnaire (PSEQ) (Nicholas MK 2007)
	Patient Acceptable Symptomatic State question (PASS) (Levy 2016, Chalal 2015)
	Patient Reported Outcomes Measurement Information System (PROMIS) Bank v2.0 Physical Function
	Tegner Activity Level Scale (TALS) (Mohtadi 2012)

A. Sample size estimation:

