All participants will be provided verbal and/or written information (depending on preference) detailing the purpose of the study, type of testing and treatment involved, and potential risks and benefits of participation. Participants will be given time to ask questions and determine their interest in participation without coercion. Patients will be informed during the recruiting process, that if they consent to study participation, they cannot receive a corticosteroid injection that day or during the 4 weeks of the trial. A 4-week follow-up visit to the physician is standard of care for patients with GTPS seen in the Jameson Crane Sports Medicine Institute. This allows physicians to evaluate the effects of common treatments like medication, injections, 'wait and see' advice, and/or physical therapy; at that time, they determine next step interventions based on the initial treatment response. Our research will work within this same 4-week 'trial' period during their regularly scheduled doctor's visits to provide one of two different types of exercise education.

Patients who refuse to forgo injections for 4 weeks will be excluded from the study. Individuals who, for medical reasons, cannot tolerate or should not assume the positions required for the exercises for any reason other than hip discomfort will be excluded. Patients must enroll on the same day as the visit with their physician in order to receive the intervention; however, they do not have to complete the REDCap questionnaires during that visit. All participants will have the option to complete their questionnaires via a unique link to their personal survey or verbally by phone; the online link will be sent to them via email to be completed at their earliest convenience. The participants will be required to sign the IRB-approved consent and HIPAA forms prior to participation in the study.

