C. Blinding: Investigators involved in the participant testing and statistical analysis of the outcome variables of interest will be blinded to group allocation. The treating physicians, physical therapist interventionists and patients cannot feasibly be blinded to treatment arm. Participants will not be informed of the study hypotheses and unblinded investigators will not share group allocation information with the blinded investigators. All references to group assignment in other research documentation (ie. REDCap™, video data collection form) will be coded (ie. '0' and '1') to maintain blinding. One trained tester will consent and perform baseline and 4-week follow-up testing. At the 4-week follow-up, the physician will re-evaluate the participant with the clinical diagnostic criteria and discuss their compliance and response to the home exercise program. As is consistent with standard of care, the physician and patient will determine the next course of treatment. The treatment plan will be entered using custom coding (ie. 'smart phrases') to allow discrete data to be queried. Statistical analysis will be performed by the blinded study biostatistician with input from the PI (see Statistical Analysis Plan). After the physician finishes his/her visit with the participant, the tester will proceed with the 4-week follow-up testing and will remind the participant she or he is blinded to treatment and cannot receive any information about the group to which they have been assigned.

D. Clinic-based testing: Baseline testing and treatment will occur in the clinic, immediately following the physician evaluation and confirmation of GTPS diagnosis, for all patients who consent to participate in the study. The clinic-based testing sessions will occur at baseline (immediately after randomization) and at the 4-week clinical visit by a blinded tester. These testing sessions will take about 10 minutes for the questionnaires. Clinic-based testing will include patient-reported questionnaires using Research Electronic Data Capture (REDCap™) survey. REDCap™ is a secure, web-based application that supports data capture, auditing, and exporting⁴⁰ to gather baseline data with regard to their pain and level of function⁴¹ and is hosted at The Ohio State University. Participants will be given the option to complete the survey on either our research handheld tablet (iPad) or laptop or desktop provided by the researcher.

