E. Intervention: The single physical therapy educational and instructional session will occur at baseline, immediately following the clinic-based testing. This session will be administered by the unblinded physical therapist interventionists who is trained to administer these protocols. **Participants will receive either (1) standard exercise education and instruction (SE) or (2) load modification education and instruction (LM), based on their treatment group randomization.** Standard exercise education includes exercises currently prescribed by physical therapists, like stretching and strengthening activities. Participants randomized to the load modification group will undergo approximately 5 additional minutes of education and instruction about their posture and movement modifications and will also be provided an information sheet with text and pictures (see Appendix: Supplements). Both groups will be instructed to perform the home exercise program once per day, performing Level 1 activities for the first two weeks and Level 2 activities for the last two weeks. (see Appendix. Supplements - Home exercise programs for both groups). Both groups will receive handouts with pictures and detailed instructions for each of their exercises.

a. Home exercise program (HEP): Both protocols were modelled after current literature for a standard lower extremity exercise program for GTPS and a load modification program. The load modification program from Mellor and colleagues (2016) was further adapted to include exercise dosage shown to be effective in

patellar tendinopathy trials.^{29,30} The HEP will be instructed and guided by the physical therapist, in combination with practice by the patient, and demonstration by the therapist, if needed. It is expected that program instruction will take about 15-20 minutes in both groups and that the home programs themselves will take between 15-20 minutes. The physical therapist will provide standardized cueing to optimize technique. Participants will be provided opportunities to ask questions during the session and provided a written home program with text and pictures for the patient to follow. These instructions, including the pictures will be made available online through REDCap™, along with instructional videos to provide the participant an additional resource to clarify technique.

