Post collection data storage and analysis: A blinded study team member will be responsible for 2D video quality control and creating trial clips for subsequent analysis. Video analysis will begin after the last participant completes their 4-week follow-up. These data will be used to determine measurement variability (intraclass correlation coefficients, standard error of the measurement, and minimal detectable change values) and provide information with regard to changes in movement patterns as a result of program participation. Frontal plane kinematics (peaks and excursions) of the trunk, pelvis, hip, and knee will be calculated (Kinovea version 0.8.15) for each task. Analysis will include the double and single leg static starting postures and peak frontal plane motion (as identified using the joint position tracking function). Lines will be drawn through the long axes of the bones for the shank and thigh, through the ASIS for the pelvis, and from the sternum to the midpoint of the ASIS line (Figure 2). Horizontal and vertical 'lab axes' will be applied to the image to allow calculations relative to pure horizontal (ie. pelvic drop) and pure vertical (ie. trunk lean). Angles will also be calculated with respect to the proximal segment.

Statistical analysis plan:

An intention to treat approach is planned for all analyses, using all participants who were randomized who have available data at 4 week follow-up. Where appropriate, normality will be assessed and non-parametric approaches will be used when assumptions are violated. Demographics and clinical characteristics (ie. age, sex distribution, BMI, baseline pain scores, etc) will be summarized for SE and LM groups, respectively, and compared between the groups using two-sample t-test for continuous outcomes or Fisher's exact test for discrete outcomes.

To evaluate the effect of treatment group allocation on dichotomized treatment success (Aim 1, Hypothesis 1), defined as either: 1) at least 'moderately better' on the Global Rating of Change scale or 2) ≥ 2 point decrease on the Numeric Pain Rating Scale, we will use Fisher's exact test to compare the success rate between SE and LM group. Frontal plane kinematics are a secondary variable of interest (Aim 1, Hypothesis 2). With the available 2D data set, we will compare change scores between groups using independent t-tests and/or effect sizes. These data may serve as preliminary data for future grant applications.

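### The baseline pain score behind the NPRS success criterion may be collected after the unblinded treatment session, and the SAP does not say which record is the baseline

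*Combined protocol and SAP*

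**What the plan says.** **Intended order.** Most of the protocol puts testing first. The Overview says the session "will be performed by a licensed physical therapist immediately after the testing procedures are complete", and section E says "The single physical therapy educational and instructional session will occur at baseline, immediately following the clinic-based testing". Section B places randomisation after testing. Section D makes the REDCap survey the source of baseline data on pain and function, and supplies a tablet or computer for it.

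**Exception.** Recruitment and Informed Consent requires enrolment on the day of the physician visit in order to receive the intervention, and continues: "however, they do not have to complete the REDCap questionnaires during that visit". Participants may answer by phone or by link: "the online link will be sent to them via email to be completed at their earliest convenience". No latest time is given, nor any condition that the answers precede the session.

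**Endpoint.** In the Statistical analysis plan, success is either a GROC rating of moderately better or above, or a "≥ 2 point decrease on the Numeric Pain Rating Scale". No record or window is named as the start of that decrease. The term "baseline pain scores" appears only among the characteristics to be summarised and compared between arms.

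**Blinding.** Section C states that "patients cannot feasibly be blinded to treatment arm". It also states a safeguard: "Participants will not be informed of the study hypotheses".

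**The concern.** A baseline score should be fixed before allocation so that treatment cannot affect it. Here a participant who uses the remote option can supply it after being randomised, instructed and told what to do about painful activity, and these instructions differ by arm (section E). That score then sets how far pain must fall to count as a success. A rating lowered by the session makes the 2-point drop harder to reach; a raised one makes it easier.

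Material bias between arms needs a further condition: either the share answering late or the shift after the session must differ by arm. The planned comparison of baseline pain between arms is also affected, because it would mix ratings given before and after treatment.

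**Working it through.** **1. Can the plan as written produce a post-treatment baseline?** The session is given at the enrolment visit (section E). The questionnaires need not be completed at that visit (Recruitment and Informed Consent). Baseline pain comes from those questionnaires (section D). Together these allow it.

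**2. Does another record fill the role?** Three other pain records exist, and none is designated as the baseline:
- the eligibility rating (Table 1), an average of at least 4/10 on most days, which is an entry threshold;
- the weekly survey NPRS (section F), which comes after treatment;
- the NPRS logged with each video task (section G), which is tied to the task.

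**3. The plan's own figure.** Inputs from section A: 20% success with standard exercise (SE), 50% with LM, one-sided alpha 0.10, power 80%, 1:1. With the pooled normal approximation:

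n = [1.2816·√(2·0.35·0.65) + 0.8416·√(0.2·0.8 + 0.5·0.5)]² / 0.30² = (0.8645 + 0.5389)² / 0.09 = 21.88, so 22 per arm.

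With 30% attrition, 22/0.7 = 31.4, so 32 per arm and 64 in all. Both figures reproduce, and this point does not change them.

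**4. How much could it matter?** The documents give no late share, shift, NPRS standard deviation or GROC–NPRS correlation. The following is illustration only. Assumptions:
- GROC and NPRS success are each a standard normal variable exceeding a common threshold t, with correlation ρ from 0.3 to 0.7.
- t solves 1 − Φ₂(t, t; ρ) = 0.50 for LM and 0.20 for SE. The marginal rates are then 32–38% and 11–13%.
- The SD of NPRS change is 2.0.
- In a late fraction f the baseline is shifted by d points, which moves only the NPRS threshold, to t ± d/SD.

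Arm success = (1 − f)·p + f·[1 − Φ₂(t, t ± d/SD; ρ)].

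Example, LM only, d = 0.5, baseline lowered: the bracket is 44.8–45.4%. At f = 25%, 0.75·50 + 0.25·44.8 = 48.7%, and with 45.4 it is 48.9%.

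| Scenario | Baseline lowered | Baseline raised |
|---|---|---|
| LM only, d = 0.5, 25% late: LM success | 48.7–48.9% | 51.5% |
| LM only, d = 0.5, all late: LM success | 44.8–45.4% | 55.9–56.1% |
| LM only, d = 1, all late: LM success | 40.7–42.2% | 62.6–62.8% |
| SE only, d = 0.5, 25% late: SE success | 19.2–19.3% | 21.1% |
| SE only, d = 0.5, all late: SE success | 16.7–17.0% | 24.4–24.6% |
| Both arms, d = 0.5, 40% late LM, 10% late SE: difference | 28.3–28.5 | 31.9–32.0 |
| Both arms, d = 0.5, 25% late in each: difference | 29.5–29.6 | 30.4 |
| Both arms, d = 0.5, all late: difference | 28.1–28.4 | 31.4–31.5 |

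The planned difference is 30 points. Over an SD of 1.5 to 2.5, the first row becomes 48.3–49.1% or 51.1–52.1%, and the third 38.5–43.4% or 59.9–67.6%. The all-late rows are outer limits.

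**5. Effect on power.** The SAP does not state the side or level of the Fisher test. At the one-sided 0.10 level of section A, with 22 per arm and SE at 20%, exact power is 69% at LM 50%, 66% at 48.7% and 72% at 51.5%. The gap from 80% to 69% comes from sizing an exact test by the normal approximation and is a separate matter. The first row of the table accounts for about 3 points either way.

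**The case against.** The strongest reply is that the intended order is clear. The Overview and sections B and E put testing before treatment, section D describes baseline testing in clinic for everyone who consents, and the remote option is a convenience mentioned under recruitment. On an ordinary reading, the 2-point drop runs from baseline testing to week 4. No harm is shown either. Bias needs late answers, a shift caused by one session, a difference between arms in lateness or shift, and success that turns on the NPRS and not on GROC. With 25% late and a 0.5-point shift in LM only, the movement is at most 1.5 points, or 0.015 × 22 = 0.33 of a participant.

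Much of this stands. The effect is probably small, withholding the hypotheses makes an arm-specific shift less likely, and the all-late scenarios are not forecasts. The NPRS recall period is not given; it bears on whether one session could move the rating at all. The Standard Operating Procedures and survey supplements were not available and may contain a timing rule.

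The reply does not remove the problem. The recruitment section is an explicit exception to the intended order. Reading the decrease as baseline to week 4 does not help when the baseline survey itself may be late.

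**Conclusion.** The concern holds and should be fixed. Following the plan as written can yield a post-treatment, unblinded baseline for one of the two routes to primary success, and the SAP does not name the score to be used.

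The size cannot be known from the documents. Under the assumptions shown, partial lateness with a half-point shift confined to one arm moves that arm's success rate by about 1 to 1.5 points; the same shift in both arms with 40% late in LM and 10% in SE moves the difference by about 2 points at most. Equal shift and equal lateness at 25% move it by about half a point or less. The case rests on an undefined and avoidably exposed reference value, not on a demonstrated large bias. Confidence is medium, because the unseen supporting documents may settle the timing.

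**What to change.** - Collect the single baseline NPRS item in clinic before the envelope is opened.
- Name that score in the SAP as the start of the 2-point decrease.
- Limit remote completion at baseline to questionnaires that do not feed the primary endpoint.
- State in the SAP how a participant without a pre-allocation NPRS is handled, without making it a bar to randomisation.
- Correct section D, which places baseline testing after randomisation, so that it agrees with section B.
- If late baselines already exist, report late completion by arm from the REDCap timestamps.
- If the Standard Operating Procedures or supplements already fix the timing, cite that rule in the protocol and SAP.

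The cost is a few sentences and about one question on the day; section D puts the whole questionnaire set at about 10 minutes. The planned sample size is unchanged. The downside is an occasional missing baseline NPRS, which the handling rule must cover.

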b. Activity modifications instructions for the load modification group: This instruction will take approximately 5 additional minutes based on our use of this handout in our physical therapy clinic with patients with GTPS for the past 2 years.

i. **Posture and movement handouts:** The physical therapist will share the handout (Appendix 2. Supplements – Lateral Hip Pain Activity Modifications) with the participant, asking them to identify any of the movements or postures (ie. sitting with legs crossed, iliotibial band stretching) that are common to their daily activities. Patients will be educated as to how each contributes to increased pressure on the lateral structures of hip and can cause pain. The physical therapist will review, demonstrate, and provide feedback on all items relevant to the participants' daily routine.

ii. **Using pain as a load modification guide:** Participants in the load modification group will be instructed not to exceed 5 out of 10 on the NPRS during the exercises, and proceed with training as long as this pain intensity during exercise does not increase their pain in within the next 24 hours.¹³

iii. **Changes to activity level:** participants in the load modification group who report >5/10 pain with exercise that does not change or is worse the next day will be advised to reduce their physical exercise activity (ie. walking, hiking, running).¹³ Participants in the load modification group will also be instructed to modify activity level as needed to avoid increasing pain or stiffness each week. Participants randomized to the standard exercise group will be instructed to avoid the painful physical exercise activity for the duration of the 4-week program (ie. "If it hurts, don't continue to do it. Focus on these few exercises for the 4 weeks). Activity level will be monitored using the Tegner Activity Level Scale on a weekly basis over the 4-week intervention.⁴³

F. Weekly online/telephone surveys: Participants will be asked to complete a REDCap™ survey (Appendix 2. Supplements – Weekly Survey) each week until their follow-up visit to the Jameson Crane Sports Medicine Institute for study testing and their clinical visit. This weekly survey will include the GROC, the NPRS, and home exercise program compliance questions. It will also include questions about any treatment they have received or injuries they have had that may affect the outcomes of interest.

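### Week-4 testing is placed both before and after the unblinded physician visit, and the baseline pain score may be recorded after treatment

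*Combined protocol and SAP*

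**What the plan says.** **Week-4 order.** The text introducing Table 2 states: "Participants will undergo the same clinic-based testing protocol at the 4-week follow-up prior to their visit with the physician". Section C (Blinding) states: "After the physician finishes his/her visit with the participant, the tester will proceed with the 4-week follow-up testing". Section C also describes what happens with the physician at week 4: "the physician will re-evaluate the participant with the clinical diagnostic criteria and discuss their compliance and response to the home exercise program". Physician and patient then settle the next course of treatment. On who knows the allocation, section C says: "The treating physicians, physical therapist interventionists and patients cannot feasibly be blinded to treatment arm". The tester and the statistician are blinded, and participants are not told the hypotheses.

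**The endpoint.** The Statistical analysis plan counts a participant as a success on either of two self-reports: a GROC of moderately better or higher, or a 2-or-more "point decrease on the Numeric Pain Rating Scale". The arms are compared by Fisher's exact test, "using all participants who were randomized who have available data at 4 week follow-up".

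**Other readings of the same scales.** Section F says of the remote survey: "This weekly survey will include the GROC, the NPRS, and home exercise program compliance questions". It is collected "each week until their follow-up visit to the Jameson Crane Sports Medicine Institute for study testing and their clinical visit". Section G adds NPRS scores stored with the video of each task.

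**Baseline order.** The text introducing Table 2, section B and section E all put testing before the treatment session. Recruitment and Informed Consent requires same-day enrolment, but does not require the REDCap questionnaires at that visit. It offers an emailed link or a phone call and sets no deadline. Section D names the REDCap survey as the source of baseline pain data. Section B randomises after testing, while section D puts baseline testing after randomisation.

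**The concern.** Both success components are the participant's own judgement, and participants know what treatment they received. A blinded tester therefore does not protect the measurement from what the participant has just heard. GROC asks how much the participant has changed. Under the section C order, an unblinded physician has covered much the same ground minutes earlier, and the two have agreed what to do next. Either part of that conversation could move the GROC and NPRS answers. Two sites, or two staff members at one site, could each follow a sentence of the protocol and collect the primary outcome under different conditions.

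The baseline matter concerns only the NPRS component, because GROC needs no baseline value. If the first NPRS is given after the education and exercise session, it is no longer a pre-treatment reference, and the 2-point criterion measures change from a different starting point.

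**Working it through.** No figure in the plan is disputed, and the sample size is unaffected. The check consists of setting the statements side by side.

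1. **Can both week-4 statements be followed?** No. One puts testing before the physician visit, the other after it. Both are current text about the same clinic testing, and nothing ranks one above the other.

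2. **Does week-4 clinic testing include GROC and NPRS?** This is an inference. The protocol lists no clinic questionnaires by name. The text introducing Table 2 describes the testing as surveys on pain and function, and Table 2 makes GROC and NPRS the primary variables. The only collection point that names GROC explicitly is the weekly survey in section F. The inference is reasonable, and the point depends on it.

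3. **Does the order matter?** Under the Table 2 text, the answers are given before the discussion and cannot be affected by it. Under section C, they follow a discussion of compliance and response with someone who is not blinded. The first order removes this exposure; the second builds it in.

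4. **Can baseline NPRS follow treatment?** Three places intend testing first. The recruitment section then permits later completion. The visit it refers to could be the physician visit alone, since the Overview starts the baseline study visit straight after the physician's examination. However, section D has baseline testing and treatment in the clinic directly after that examination, so a participant who answers an emailed link after leaving would normally have been treated already. No section sets a deadline or exempts the NPRS item.

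5. **What does a late baseline do to the criterion?** Let P be the pre-treatment NPRS, W the week-4 NPRS, and P + s the late recorded baseline. Success requires (P + s) − W ≥ 2, that is, P − W ≥ 2 − s. If early relief lowers the recorded baseline (s < 0), success becomes harder to reach; if pain after the session raises it (s > 0), easier. The documents give no value for s, and participants who meet the GROC criterion are unaffected.

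6. **Is the week-4 reading identified?** Largely. The SAP refers to data at 4-week follow-up. In the Table 2 text, section C and section H that phrase means the clinic visit. Some ambiguity remains because the SAP's Aim 2 text calls the weekly surveys follow-up surveys.

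**The case against.** The strongest reply is that no bias has been demonstrated. Both arms have the same physician visit, participants are not told the hypotheses, and they are unblinded whichever order is used. They have also been asked for GROC and NPRS in the weekly surveys, so the clinic answer is not their first. All of this stands, and it limits the point to avoidable exposure.

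A reader might go further and infer that the section C order favours the load modification arm. The documents do not support that. An unblinded physician makes a difference between arms possible, but nothing gives its direction or size.

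A reader might also infer that baseline scores will routinely be taken after treatment. That too goes beyond the text. The explicit statements intend the reverse, and the deferral appears in recruitment wording whose reference to a visit can be read narrowly. What stands is that later completion is permitted without limit.

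A third tempting reading is that the SAP leaves the week-4 endpoint undefined. As step 6 shows, the clinic reading is the natural one, and a clarifying sentence is enough.

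Finally, the disagreement between sections B and D on randomisation and baseline testing might suggest that concealment fails. It does not follow: allocation is coded and the envelopes are sealed until the therapist opens one.

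**Conclusion.** The point holds and should be fixed. The contradiction over week-4 order is explicit, and confidence in it is high. Its relevance to the primary endpoint rests on the inference that clinic testing includes GROC and NPRS. Confidence is moderate that the baseline NPRS may be recorded after treatment, because this rests on a permission that conflicts with the intended order. Confidence is also moderate that the readings need naming, which is a clarification only.

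The size of any effect cannot be stated. The documents contain nothing from which to estimate how far the physician discussion or a late baseline would move the success rate in either arm. The case for change is that the exposure is written into the plan, concerns a self-reported primary endpoint, and can be removed at almost no cost.

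**What to change.** 1. Adopt the order in the text introducing Table 2: week-4 GROC and NPRS are completed before the physician visit. Correct section C to match.
2. Exempt the baseline NPRS item from the deferral in Recruitment and Informed Consent. Require it before the envelope is opened, asked verbally by the blinded tester if the full survey is postponed. In section D, delete the parenthesis that puts baseline testing after randomisation, so that it agrees with section B.
3. As a clarification, state in the SAP that success uses the pre-treatment baseline NPRS and the week-4 clinic GROC and NPRS taken before the physician visit, not the weekly-survey or video-task readings.

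Optionally, add a sensitivity analysis that takes GROC and NPRS from the last weekly survey before the visit for all participants in both arms. The data are already planned.

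The cost is a wording change and a small change in visit flow. A few minutes of questionnaires move earlier in each visit, and participants lose a little flexibility. Requiring only one item at baseline keeps the burden on same-day enrolment small.
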